### **10.2.3 6MWT**

For distance walked in the 6MWT of the subset of ambulatory subjects, observed values, absolute changes from baseline, and percent changes from baseline will be listed and summarized. A summary table will include p-values for treatment group comparisons of changes from baseline. Because of potential differences in 6MWT administration procedures across study sites, “site” will be carefully considered as a potential source of excess variation and will be included in the statistical model as a random effect if warranted.

## **10.3 QoL**

The following QoL measurement instruments, although routinely used for DMD trials, have not been validated for young adults, and this trial will enroll subjects > 18 years old.

#### **10.3.2 Pediatric Outcomes Data Collection Instrument (PODCI)**

The PODCI consists of 83 items and results in both standardized and normative scores for each of 6 scales. Decreasing scores over time indicate improvement. Separate inventories are used for subjects and for parent responders. While responses to all 83 items will be listed, only the 6 scales will be summarized. Summary tables and listings will include observed values and changes from baseline; tables will also include p-values for treatment group comparisons of change from baseline.

[figure not shown]
CCI

CCI

CCI

## 11. OTHER DATA COLLECTED

### 11.1 Missed Visits and Assessments

A listing of missed visits and assessments will show visit and/or assessment missed.

### 11.2 Protocol Violations/Deviations

Protocol excursions will be classified as either violations or deviations. Per ICH E3 (Structure and Content of Clinical Study Reports), violations will be defined as:

- Enrolling into the trial without meeting all inclusion/exclusion criteria and without obtaining a waiver for any deviations from the protocol-defined entry criteria;
- Continuing in the trial after developing a withdrawal criterion (see Protocol Section 7.10);
- Receiving an incorrect dose or incorrect treatment; or
- Taking a prohibited concomitant medication (see Protocol Section 5.5).

Subjects with protocol violations will be excluded from the per protocol population. All other protocol discrepancies will be considered deviations and will be categorized for purposes of

---

summarization. Some protocol deviations may prohibit subjects from being in the per protocol population; this will be determined on a case-by-case basis before database lock.

In addition to the listings of inclusion/exclusion criteria detailed in [Section 8.2](#) and missed visits and assessments detailed in [Section 11.1](#), a separate listing will show all other protocol violations and will include protocol version, the category of the violation (to be determined), and an indicator for per protocol exclusion. Frequency and percentage of subjects in each violation category and excluded from the per protocol population will be summarized.

## 12. CLINICAL EVENTS COMMITTEE

In order to apply some level of consistency and standardization, the following will be adjudicated by a CEC:

- Clinical event endpoints
- AEs occurring within 24 hours of IP administration or reference time point (peri-procedural AEs)
- AEs judged by the investigator as possibly, probably or definitely related to the IP or IP administration procedure (related AEs)
- Treatment-emergent SAEs

The CEC will follow consensus definitions of cardiovascular endpoint events. In the case where the protocol explicitly provides an endpoint definition, the CEC will adjudicate the clinical event according to the protocol definition and then, separately, according to the consensus definition. In the case where the protocol provides only a partial definition (e.g., “emergency room treatment for heart failure”) or is silent on the definition of the endpoint, the consensus definition, if it exists, will be used.

For safety endpoints, a hierarchy will be applied for a clinical event that could be adjudicated in multiple categories so that a clinical event is counted only once. The hierarchy, from highest severity to lowest, will be death > heart failure hospitalization > cardiovascular-related hospitalization.

For any AE submitted to the CEC, all of the above characteristics will be adjudicated. In addition, the CEC can combine AEs reported separately into a single AE, can change the event description (i.e., the term used to report the AE), and can change the status of the reported event to a non-AE.

Any adjudicated event not otherwise named in the consensus definitions, as well as changed event descriptions, will be MedDRA-coded.

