### **2.3 Study Assessments**

#### **2.3.1 Safety Assessments**

Safety will be assessed at 6 and 12 months post infusion or reference date unless otherwise noted. For usual care subjects, the reference time point will be randomization date + 7 days at 9:00 a.m. (subject's local time).

1) Adjudicated clinical events:

- a) The following events occurring during or post infusion or reference time point:

- For subjects who receive CAP-1002 only, new TIMI flow 0-2 or TIMI myocardial perfusion grade (TMPG) 0-2, noted immediately following intracoronary infusion of investigational product (IP) and persisting > 3 min after IP infusion, despite intracoronary vasodilator administration.
- Within 72 hours of intracoronary infusion or reference time point, sudden unexpected death defined as occurring within 1 hour of symptom onset, or unwitnessed death in a person previously observed to be well within the preceding 24 hours without an identified cause.
- Major adverse cardiac events (MACE) within 72 hours of intracoronary infusion or reference time point, including death, non-fatal myocardial infarction and hospitalization for cardiovascular event (including heart failure hospitalizations). Evidence of myocardial injury will be assessed by a rule out myocardial infarction (MI) cardiac enzyme protocol following IP administration. Among subjects who receive CAP-1002, troponin and creatine phosphokinase MB isoenzyme (CK-MB) will be obtained every 8 hours for 20-24 hours after IP infusion.

b) Sudden unexpected death defined as occurring within one hour of symptom onset, or unwitnessed death in a person previously observed to be well within the preceding 24 hours without an identified cause.

c) MACE, including death, non-fatal myocardial infarction, hospitalization for cardiovascular event (including heart failure hospitalizations), emergency room treatment for heart failure, left ventricular assist device or heart transplant.

d) Any hospitalization due to a cardiovascular cause.

e) Any inter-current cardiovascular illness which prolongs hospitalization.

f) Development of, or an increase in the frequency of, ventricular tachycardia (VT) with duration of 30 seconds or longer ascertained by protocol mandated continuous cardiac monitoring via Holter Monitor or ZIO® Patch.

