## 4. SAMPLE SIZE

The sample size of approximately 12 subjects per treatment group is adequate to assess safety and tolerability and to explore efficacy.

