### 9.1 Adjudicated Clinical Events

Clinical events, described in [Section 2.3.1](#), will be adjudicated by an independent Clinical Events Committee (CEC) (see [Section 12](#)). Each event will be summarized as frequency and percentage of subjects who experienced the event. In addition, a composite event will be defined as new TIMI flow 0-2 or TMPG 0-2 (CAP-1002 subjects only), sudden death, or MACE during or following IP administration or reference time point. For the composite and its components, summaries will include exact 90% confidence intervals (CIs) for both treatment groups. For peri-procedural events other than TIMI flow 0-2 or TMPG 0-2, summaries will include a 90% CI for the difference in proportions between treatment groups, and the one-sided p-value from an exact binomial test of the difference between treatment groups. For all other clinical events, assessed over the length of the trial, event rates per 100 subject-years will be calculated and, if applicable, treatment groups will be compared using negative binomial regression with an offset for days of follow-up (log transformed). If the dispersion parameter is not significantly different from zero, Poisson regression will be used instead.

For the analysis of development of increased HLA antibodies to HLA antigens specific to the CAP-1002 donor, incidence of increased HLA antibody levels specific to the donor will be summarized and analyzed; for usual care subjects, a random donor will be selected from those that were matched to the subject during screening. Elevated levels of donor specific antibodies will also be summarized and analyzed by time point for all nominal time points at which samples were collected for DSA testing. Analyses will be performed using both 1000 and 5000 MFI as the threshold for defining increased HLA antibodies.

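### Read literally, the count-once hierarchy in SAP section 12 takes heart failure admissions out of the safety endpoint that covers all cardiovascular hospitalizations

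*SAP*

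**What the plan says.** SAP section 12 sets the rule for safety endpoints as a group. Where an event qualifies for more than one category, it is placed by rank in a hierarchy, "so that a clinical event is counted only once". The order given is "death > heart failure hospitalization > cardiovascular-related hospitalization". Nothing in the section limits this to MACE or to any one table.

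SAP 2.3.1 lists, as item 1(d) and separately from MACE in item 1(c), "Any hospitalization due to a cardiovascular cause". Protocol 3.3 has the same endpoint as item 3 of its six- and twelve-month list. Neither document makes an exception for heart failure or fatal admissions.

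The MACE definition in SAP 2.3.1 treats heart failure admissions as one kind of cardiovascular admission: "hospitalization for cardiovascular event (including heart failure hospitalizations").

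SAP 9.1 sets the analysis of these endpoints. "Each event will be summarized as frequency and percentage of subjects who experienced the event". It adds: "For all other clinical events, assessed over the length of the trial, event rates per 100 subject-years will be calculated", with a negative binomial or Poisson comparison of the arms where applicable.

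**The concern.** By the SAP's own MACE wording, every heart failure admission is a cardiovascular admission and so meets 1(d). Section 12 nevertheless moves it to a higher category and counts it only there. An endpoint defined to include every cardiovascular admission would then report only those left after the more serious ones, on the SAP's own severity order, had been taken out.

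Safety is the primary objective. Clinical event endpoints go to the DSMB (SAP section 14), and Appendix B plans a table of other clinical safety endpoints. A reader of that table would take the 1(d) row at face value. SAP section 15, which records departures from the protocol's statistical methods, lists only the mITT definition, so no narrowing of 1(d) is declared. Heart failure hospitalization, which receives the moved event, is not an endpoint of its own in SAP 2.3.1, so a reclassified admission leaves 1(d) with no stated row to go to.

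**Working it through.** The plan gives no event count or rate for 1(d), so there is no figure to reproduce. The check traces the rule and then shows its arithmetic on assumed event mixes.

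**Step 1: trace each type of event.**

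- *Non-fatal heart failure admission.* It meets 1(d) under SAP 2.3.1. It also fits the heart failure tier in section 12, which outranks cardiovascular-related hospitalization. Counted once, it is lost to 1(d).
- *Cardiovascular admission followed by death.* It meets 1(d). It moves to the death tier only if the CEC regards the admission and the death as one clinical event. Ranking death first suggests this. However, section 12 only permits the CEC to combine separately reported events; it does not require it.
- *Other cardiovascular admission.* It fits only the lowest tier and stays in 1(d).

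**Step 2: formulas.** Let T be all cardiovascular admissions in an arm, h the non-fatal heart failure admissions, and f the fatal admissions that the CEC merges with the death.

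- Count as defined in SAP 2.3.1: T
- Count under the literal hierarchy: T − h − f
- Share reclassified: s = (h + f)/T
- Event rate under the hierarchy = rate as defined × (1 − s)

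The multiplier is 0.75, 0.50, 0.25 and 0 for s = 25%, 50%, 75% and 100%. These values of s are assumptions. If s is the same in both arms, the rate ratio is unchanged. Otherwise it is multiplied by (1 − s in the CAP-1002 arm)/(1 − s in the usual care arm).

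**Step 3: illustrations.** Inputs are about 12 subjects per arm (SAP section 4) and 12 months of follow-up (SAP section 3), so 12 × 1 = 12 subject-years per arm if follow-up is complete. Each mix assumes one admission per subject, and that fatal admissions are merged with the death. Under these assumptions the percentage of subjects and the rate per 100 subject-years are the same number.

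| Assumed admissions in one arm | As defined | Literal hierarchy |
|---|---|---|
| 1, heart failure | 1/12 = 8.3 | 0/12 = 0 |
| 3, of which 1 heart failure | 3/12 = 25.0 | 2/12 = 16.7 |
| 3, of which 1 heart failure and 1 fatal | 3/12 = 25.0 | 1/12 = 8.3 |
| 4, of which 2 heart failure and 1 fatal | 4/12 = 33.3 | 1/12 = 8.3 |

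The exact 90% interval in the first row is 0.4% to 33.9% as defined and 0% to 22.1% under the hierarchy. (SAP 9.1 plans such intervals for the composite and its components. They are shown here for 1(d) only to illustrate.)

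**Step 4: subjects versus events.** The rate falls with every reclassified admission. The percentage of subjects falls only when the subject has no other qualifying cardiovascular admission. Each such subject lowers it by 1/12 = 8.3 percentage points.

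**Step 5: what is not affected.** Death, heart failure hospitalization and cardiovascular hospitalization all lie within MACE, so moving an event among them does not reduce total MACE. The composite in SAP 9.1 contains MACE and is likewise not reduced. The admissions also stay in the treatment-emergent SAE tables and listings.

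**The case against.** The best counter-argument is that the hierarchy was meant only to sort overlapping MACE components. Its tiers look like MACE components: heart failure hospitalization is named in SAP 2.3.1 only inside the MACE definition, and death is named there as a component. A rule that ran across endpoints would also be unworkable. Every cardiovascular admission is both MACE and 1(d), a sudden death is both item 1(b) and MACE, and the hierarchy ranks neither pair. Non-fatal MI, assist device, transplant and emergency-room heart failure treatment are not ranked either, which suggests a narrow purpose. SAP 9.1 points to inclusive counting, and section 12 tells the CEC to adjudicate by the protocol's definition where one is explicit.

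Much of this stands. The narrow reading is plausible and may be what was intended, and under it 1(d) loses nothing. But the SAP does not say so. The rule is addressed to safety endpoints in general, its lowest tier matches 1(d), and no sentence returns heart failure admissions to 1(d). Adjudicating by the protocol's definition does not resolve the matter: it makes a heart failure admission eligible for two categories, which is the case the hierarchy then settles. SAP 9.1 conflicts with section 12 but does not override it, so two programmers could produce different 1(d) tables from the same data.

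A reader might infer three stronger things that the documents do not support:

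- *That fatal admissions are certainly removed.* This depends on a CEC decision that no rule prescribes.
- *That the 1(d) rate is understated by a known amount, such as 30% to 70%.* Any such figure only restates an assumed share; the documents give no event mix.
- *That the trial's safety reporting as a whole understates harm.* Total MACE, the composite and the SAE tables and listings lose nothing.

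**Conclusion.** Wrong as written, with limited reach. Applied literally, section 12 gives a count for 1(d) that contradicts the endpoint's definition in SAP 2.3.1 and protocol 3.3, and the subject-level summary in SAP 9.1. Heart failure admissions are removed on the text alone; fatal cardiovascular admissions are removed only if the CEC merges admission and death.

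The size cannot be fixed from the documents because s is unknown. The error is confined to the 1(d) row and any component-level rows. The 8.3-point step rests on about 12 subjects per arm, and the illustrated rates also assume complete 12-month follow-up and one admission per subject.

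**What to change.** Amend SAP section 12 before database lock. Limit the count-once hierarchy to the MACE count, or to a breakdown of MACE components by worst event. State that endpoint 1(d) counts every adjudicated hospitalization with a cardiovascular cause, including heart failure and fatal ones, whatever its place in the hierarchy.

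The cost is about one sentence of SAP text. It needs no new data, because the CEC already adjudicates these events. The change is worth making under either intent: if the rule was meant broadly, it contradicts 1(d); if it was meant narrowly, the limit is missing.

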## **13. SEQUENCE OF PLANNED ANALYSES**

### **13.1 Interim Safety Reviews**

The DSMB will conduct an interim safety review after all subjects in Group 1 have completed at least 72 hours of observation (or withdrawn) and will make a recommendation on proceeding to Group 2 enrollment. Thereafter, the DSMB will conduct interim safety reviews at least every 6 months. For each DSMB meeting, the clinical study database will be reviewed, all data queries will be submitted to sites and resolved if possible, and a cut of the database will be taken on a specified date and used to produce TFLs for the DSMB.

### **13.2 Administrative Interim Analyses**

#### **13.2.1 Pre-Month 6**

An administrative interim efficacy analysis will be performed when Month 6 MRI assessments are available for at least 14 subjects. Results from the interim efficacy analysis will be used for business planning activities to assure availability of therapeutic product and to plan subsequent clinical trials and will have no effect on the design or conduct of the trial. As such, there will be no statistical penalty applied to the final efficacy analysis as a result of the interim efficacy analysis. Personnel with access to unblinded data and analysis results will be detailed in an unblinding memorandum to be filed in the Trial Master File and to be submitted to regulatory agencies. Unblinded interim data and analysis results will be kept confidential from other company personnel involved with the trial conduct and from investigators, patients, and their families.

#### **13.2.2 Month 6**

An administrative interim efficacy analysis will be performed when all subjects in the mITT population have completed the Month 6 visit or have discontinued from the study. Results from the interim efficacy analysis will be used for business planning activities to assure availability of therapeutic product and to plan subsequent clinical trials and will have no effect on the design or conduct of the trial. As such, there will be no statistical penalty applied to the final efficacy analysis as a result of the interim efficacy analysis. A safety review similar to those done for the DSMB will also be done at this time. Top line results of the Month 6 administrative interim analysis will be reported publically. Clinical site trial personnel engaged in trial conduct and data collection will remain blinded to the complete interim data and analysis results, including patient level data. Imaging Core Lab personnel will remain blinded to treatment assignment and to all non-imaging patient level data until the final 12 month analyses.

### **13.3 Final Analysis**

The final analysis will occur when all subjects have reached EOS (completed the Month 12 visit or discontinued), all clinical data have been entered into the data capture system, AE and concomitant medication data have been coded, quality control checks have been completed, all data queries have been resolved, protocol violations and the per protocol population have been identified, and the database has been locked.

## 14. DSMB

The DSMB will be appointed by the sponsor and will consist of physicians and at least one biostatistician who have no formal involvement or conflict of interest with the subjects, the sponsor, the investigators, or the clinical sites. The DSMB will communicate their findings directly to the sponsor.

Data on the following, in the form of TFLs and/or narratives, will be provided to the DSMB for review:

- Subject disposition
- Demographic and other baseline characteristics
- IP administration details
- Clinical event endpoints
- Treatment-emergent AEs and SAEs
- Safety laboratory evaluations
- Concomitant cardiac and steroid medications
- Continuous cardiac monitoring

In addition, the DSMB will be provided with TFLs from the Month 6 administrative interim efficacy analysis.

## 15. DEVIATIONS FROM STATISTICAL METHODS IN THE PROTOCOL

Section 9 of the protocol defines the mITT population differently than the SAP, as follows:

Protocol	Deviation
Modified ITT (mITT) Population: Subjects in the CAP-1002 treatment group who received the IP, and all subjects in the usual care treatment group who remain on study as of 9:00 am (subject's time zone) on Day 0.	Modified ITT (mITT) Population for Efficacy Parameter X: Subjects in the safety population who have at least one post-baseline observation for Parameter X.

## APPENDIX A: SCHEDULE OF EVENTS

Procedure / Event	Screening	Infusion		Week 2	Week 6	Month 3	Month 6	Month 12	Early Termination 
Study Day	Day -30 to -1	Day 0		Day 14 ( $\pm 3$ )	Day 40 ( $\pm 7$ )	Day 90 ( $\pm 7$ )	Day 180 ( $\pm 14$ )	Day 360 ( $\pm 30$ )	As Needed
		PRE	POST						
Informed Consent	X								
Eligibility Assessment	X	X							
Demographics	X								
Medical History	X	X							
Cardiac History	X	X							
Concomitant Medications	X	X	X	X	X	X	X	X	X
Vital Signs	X	X	X	X	X	X	X	X	X
Weight	X						X	X	X
12-Lead ECG	X	X	X	X	X	X	X	X	X
Limited Physical Examination	X							X	X
Cardiac Physical Examination	X	X	X	X	X	X	X	X	X
Cardiac MRI	X						X	X	X
24-Hour Ambulatory ECG via Holter Monitor or ZIO® Patch	X		X		X		X	X	X
Clinical Laboratory Tests (includes Chemistry, Hematology, Urinalysis)	X	X	X	X	X	X	X	X	X
Serology 	X								
Osteopontin	X			X	X	X	X	X	X
ST2	X			X	X	X	X	X	X
IL-10	X			X	X	X	X	X	X
Galectin-3	X			X	X	X	X	X	X
Exploratory Biomarkers	X			X	X	X	X	X	X
HLA	X								

Procedure / Event	Screening	Infusion		Week 2	Week 6	Month 3	Month 6	Month 12	Early Termination 
Study Day	Day -30 to -1	Day 0		Day 14 (±3)	Day 40 (±7)	Day 90 (±7)	Day 180 (±14)	Day 360 (±30)	As Needed
		PRE	POST						
DSA	X			X	X	X	X	X	X
ELISpot		X			X				
PUL scale	X				X	X	X	X	X
6MWT	X				X	X	X	X	X
Pediatric QL Inventory	X				X	X	X	X	X
PODCI	X				X	X	X	X	X
Spirometry	X				X	X	X	X	X
Coagulation		X							
Serum Troponin & CK-MB		X	X	X			X	X	X
Intracoronary Infusion			X						
Adverse Event Assessment	X	X	X	X	X	X	X	X	X

 Early Termination Visit procedures to be completed at time of withdrawal, should subject be withdrawn before Month 12 Visit. A Cardiac MRI will be conducted provided the subject's most recent study-related Cardiac MRI was conducted at least three months (i.e., 12 weeks) prior to the Early Termination Visit.

 Serology includes HIV and hepatitis testing

## APPENDIX B: TABLES OF CONTENTS FOR TABLES, FIGURES, AND LISTINGS

### TABLES

#### STUDY POPULATION

- 14.1.1 Number of Subjects by Study Visit
- 14.1.2 Subject Disposition
- 14.1.3.1 Inclusion/Exclusion Criteria Not Met
- 14.1.3.2 Protocol Violations
- 14.1.4 Analysis Populations
- 14.1.5 Demographics and Baseline Characteristics
- 14.1.6.1 General Medical History
- 14.1.6.2 Cardiac Medical History
- 14.1.7 Screening Labs
- 14.1.8 Investigational Product Administration

